### **2. Protocol version:**

Mar-2017.

### **3. Funding:**

The trial will be self funded by the main researcher.

# Introduction

- **Scientific background:**

Dental caries is a disease that affects both children and adults. Though it has a known etiology which can be prevented and controlled, it remains a major health concern in industrialized and developing communities. It is dependent on dental plaque stagnation on the tooth surface. The bacterial constituents of the dental plaque are responsible for the metabolic activity needed for the development of carious lesion and demineralization of tooth structure. However, caries can be arrested if the biofilm is controlled but that mainly occurs at the tooth surface, as in the cavitated lesions there is a difficulty in hindering or disorganizing the bacterial biofilm.

Therefore, restorative intervention is needed which implicates the removal of carious tissue followed by restoration of tooth to regain surface integrity that enabling efficient removal of dental plaque.

Traditional restorative techniques involve complete removal of carious dentin this is based on assumption that complete elimination of bacteria by complete caries removal is a must for the success of restoration. Also it may lead to extensive tooth loss and pulp exposure especially in deep caries teeth.

Another technique is step wise excavation in which partial removal of carious dentin is made and the cavity sealed in the first visit till formation of tertiary dentin then a second visit is mandatory to remove the remaining carious tissue which adds additional cost and effort in the procedure.

Moreover, there is several evidence indicating that total removal of carious tissue is not required to reach an arrested lesion state. Thereby partial caries removal

technique is approached which is less invasive and aims at leaving the deeper layer of carious dentin followed by permanent restorative material. The main target of this technique is that these deeper layer of carious dentin will be arrested and layoff of tertiary dentin is stimulated with subsequent dentinal sclerosis, thus either the possibility of pulp exposure or additional procedures during reentry of the cavity is eliminated.

However, by leaving a layer of carious dentine which contain viable bacteria, there is a liability for caries to stay active and even progress further. In addition to the sealing achieved by the restorative material, an application of antibacterial agent that reduce bacterial load, slow or arrest the present lesion will ensure the success of the partial caries removal technique.

- **Statement of the problem:**

The aim of partial caries removal technique is to eliminate the problems of complete caries removal and step-wise excavation by leaving the deeper layer of carious dentin. This will help in arresting the lesion with subsequent remineralization of the infected dentin. However; leaving bacterial infected dentine may lead to recolonization and subsequent recurrent caries.

Therefore, the application of an antibacterial agent prior to restoration of deep carious molar that eradicates viable bacteria in the remaining carious layer and aids in arresting carious lesion will ensure the success of the partial caries removal technique. Chlorhexidine is one of the most commonly used antibacterial agent. However, the use of chlorhexidine has some potential drawbacks like altered taste sensation, staining of teeth, and development of resistant bacteria that undermine its application.

Several innovative approaches were made into developing antimicrobial agents that have bacteriostatic and bactericidal effects on the bacteria responsible for developing dental caries that may have a role in arresting carious lesions. A new agent which proven to be successful as antibacterial and in arresting existing caries is nano silver fluoride which is a new formulation that composed of silver nanoparticles, chitosan and fluoride that combines preventive and antimicrobial properties. This new formulation was proven to be safe and has shown good antimicrobial properties against cariogenic bacteria which helps in arresting carious lesion.

▪ **Rationale:**

The purpose of this study is to evaluate the antibacterial effect of nano silver fluoride solution on the carious dentin. This new formula is a promising anti-caries agent with low toxicity and ease of application in addition to its antimicrobial effect. This agent could help in caries arrest and decrease in the occurrence of secondary caries.

➤ **External validity:**

**Benefits to patients/population:**

1. Preserve pulp vitality.
2. Decrease the incidence of secondary caries.
3. Time and cost effective methods.

**Benefits to practitioners/clinicians:**

1. Noninvasive and conservative.
2. Avoid unnecessary removal of dentin tissues.
3. Time and money saving.

➤ **Objectives :**

The intention of this study is to evaluate the antibacterial action of nano silver fluoride solution application against oral streptococci mutans in comparison to chlorhexidine solution after partial caries removal in class I carious permanent molars.

➤ **Hypothesis:**

The null hypothesis tested in this study, that there is no difference between nano silver fluoride and chlorhexidine application on the bacterial count of oral streptococci mutans after partial caries removal in class I carious permanent molars.

➤ **Trial design:**

This investigation will be a randomized controlled clinical trial (RCT).

➤ **Trial type:**

Parallel study design.

➤ **Trial framework:**

Equivalence trial

➤ **Allocation ratio:**

1:1.

# **Review of literature**

➤ **Search strategy:**

- **Source:**

The results have been searched in two data bases:

➤ PubMed database and Scopus database.

- **Date:** 16\03\2017

Index terms	Mesh terms
Deep carious lesion	Dentin caries Carious dentin
Nano silver fluoride	
Chlorhexidine	Chlorhexidine Chlorhexidine gluconate Chlorhexidine Hydrochloride Chlorhexidine Acetate Chlorhexidine thymol Chlorhexidine bigluconate Chlorhexidine digluconate
Bacterial count	Bacterial count Bacterial counts Bacterial load Microbiological analysis Microbial colony count Microbial colony counts  Microbial colony forming units assays

	Microbial colony-forming units assays
--	---------------------------------------

➤ **Inclusion and exclusion criteria**

Inclusion Criteria	Exclusion criteria

 
• Articles based on clinical trials that report the antibacterial effect of nano silver particles.
 
• Articles published in English
 
• Articles published after 2006
 
	
 
• Articles based on any other assessment method.
 
• Any other antibacterial agent used.
 
• Articles published in any other language.
 
• Articles published before 2006
 

	Search terms	Medline	Scopus
P	Dentin caries OR Deep cavities OR	52870	4409

	Deep caries lesion OR Carious dentin		
I	Nano silver fluoride OR NSF OR Nano silver OR Silver nanoparticles OR Silver nanoparticle OR Silver nano	19116	178478
C	Chlorhexidine OR CHX OR Chlorhexidine gluconate OR Chlorhexidine Hydrochloride OR Chlorhexidine Acetate OR Chlorhexidine thymol OR Chlorhexidine bigluconate OR Chlorhexidine digluconate	11640	3250
O	Bacterial count OR Bacterialcounts OR Bacterial load OR Microbiological analysis OR Microbial colony count OR Microbial colony counts OR Microbial colony forming units assays OR Microbial colony-forming units assays	553619	1770
P& I	((((Dentin caries) OR Deep cavities) OR Deep caries lesion) OR Carious dentin)) AND (((((NSF) OR Nano silver) OR Silver nanoparticles) OR Silver nanoparticle) OR Silver nano) OR Nano silver fluoride)	56	94

P & C	(((((Dentin caries) OR Deep cavities) OR Deep caries lesion) OR Carious dentin)) AND (((((Chlorhexidine thymol) OR Chlorhexidine digluconate) OR CHX) OR Chlorhexidine) OR chlorhexidine gluconate) OR Chlorhexidine Hydrochloride) OR Chlorhexidine Acetate) OR Chlorhexidine bigluconate)	785	0
P & I&O	(((((Dentin caries) OR Deep cavities) OR Deep caries lesion) OR Carious dentin)) AND (((((NSF) OR Nano silver) OR Silver nanoparticles) OR Silver nanoparticle) OR Silver nano) OR Nano silver fluoride)) AND ((((((Microbial colony counts) OR Microbial colony-forming units assays) OR Microbial colony forming units assays) OR Bacterial count) OR Bacterial counts) OR Bacterial load) OR Microbiological analysis) OR Microbial colony count)	15	3
P&C&O	(((((Dentin caries) OR Deep cavities) OR Deep caries lesion) OR Carious dentin)) AND (((((Chlorhexidine	227	0

	thymol) OR Chlorhexidine digluconate) OR CHX) OR Chlorhexidine) OR chlorhexidine gluconate) OR Chlorhexidine Hydrochloride) OR Chlorhexidine Acetate) OR Chlorhexidine bigluconate)) AND ((((((Microbial colony counts) OR Microbial colony- forming units assays) OR Microbial colony forming units assays) OR Bacterial count) OR Bacterial counts) OR Bacterial load) OR Microbiological analysis) OR Microbial colony count)		
P& I& C& O	(((((Dentin caries) OR Deep cavities) OR Deep caries lesion) OR Carious dentin)) AND (((((NSF) OR Nano silver) OR Silver nanoparticles) OR Silver nanoparticle) OR Silver nano) OR Nano silver fluoride)) AND ((Chlorhexidine OR CHX OR Chlorhexidine gluconate OR Chlorhexidine Hydrochloride OR Chlorhexidine Acetate OR Chlorhexidine thymol OR Chlorhexidine bigluconate OR	0	0

	Chlorhexidine digluconate))) AND ((((((Microbial colony counts) OR Microbial colony-forming units assays) OR Microbial colony forming units assays) OR Bacterial count) OR Bacterial counts) OR Bacterial load) OR Microbiological analysis) OR Microbial colony count)		
--	---	--	--

➤ **Review of studies:**

*dos Santos et al 2014*, conducted a randomized controlled clinical trial to evaluate the effectiveness of a Nano Silver Fluoride (NSF), applied once a year to arrest caries in children. One hundred thirty decayed primary teeth were randomly divided into two groups: NSF as the experimental agent and water as the control group. Teeth were clinically diagnosed and treated by one masked examiner and followed up at seven days and five and 12 months by another calibrated examiner who was blinded to the type of treatment. The criteria of the ICDAS II were followed to determine the activity of lesion and the diagnosis of caries. The Pearson's chi-square test was used to compare the groups during different follow-up exams. At seven days, 81% of teeth in the NSF group exhibited arrested caries, whereas in controls, no teeth had arrested decay ( $p < 0.001$ ). After five months, the NSF group had 72.7% with arrested decay, and the control group had 27.4% ( $p < 0.001$ ). At 12 months, 66.7% of the lesions treated with NSF were still arrested, while the control group had 34.7% remaining arrested ( $p = 0.003$ ). The number need to treat at five months was two, and at 12 months, the number was three. It was stated that NSF formulation is effective to arrest active dentine caries and not stain teeth.

**Fahadian et al 2016**, evaluated the effect of silver nanoparticles incorporated into acrylic baseplates of orthodontic retainers on *Streptococcus mutans* colony-forming units. The main outcome was to compare the number of *S mutans* colony-forming units between two groups of orthodontic patients at the debonding stage, in which one group wore orthodontic retainers which have silver nanoparticles incorporated into their acrylic baseplates while the other group received conventional orthodontic retainers. Swab samples were taken from the maxillary palatal side from the patient in the dental chair at retainer placement (T1, 1 week after debonding the fixed orthodontic appliance) and T2, 7 weeks later. Twenty-nine patients in the control group and 32 in the intervention group were analyzed. At T1, the intervention group had higher *S mutans* colony counts relative to the control group. Later, at T2 after 7 weeks there was a significant reduction of colonies in the intervention group. Finally it was concluded that adding silver nanoparticles to the acrylic plate of retainers had a strong antimicrobial effect against *S mutans* under clinical conditions.

**Salas-López et al 2017**, directed an experimental and clinical trial to evaluate the effects of pit and fissure sealant mixed with silver nanoparticles on dental caries, by means of monthly measurement of fluorescence with DIAGNOdent over six months. In the experimental phase, the adhesion and microleakage of the pit and fissure sealant experiment were evaluated. Two groups of 10 teeth, without serious carious lesions, were included. Group A received conventional Clinpro pit and fissure sealant (3M Espe, St. Paul, MN, USA), and group B received NNPs mixed with Clinpro pit and fissure sealant. For the clinical phase, a split-mouth study double blind clinical trial was performed on 40 children aged 6-10 years old with healthy, erupted permanent first molars. A conventional pit and fissure sealant or a

silver nanoparticle-mixed sealant was randomly placed. Repeated measures analysis was performed to detect presence of carious lesions was assessed using a pen-type laser fluorescence device, the DIAGNOdent pen (Kavo, Biberach, Germany). Conventional sealant presented an average microleakage of 30.6%, and the silver nanoparticle-mixed sealant showed 33.6% (P=NS). A three times greater reduction in fluorescence was found in the silver nanoparticles group compared to the conventional group (P<0.05). It was concluded by the author that silver nanoparticle-mixed sealant reduced tooth demineralization significantly and likely increased remineralization, compared to the conventional sealant.

**Aim of the study:**

The aim of this study is to evaluate the antibacterial action of Nano Silver Fluoride solution application in comparison to Chlorhexidine solution after partial caries removal in class I carious permanent molars.

**PICOTS:**

**P**= Deep class I carious molars.

**I**= Nano silver fluoride (Prepared in Nanotech Co., Egypt).

**C**=Chlorhexidine2 % solution (Cavity Cleanser, Bisco, USA).

**O** = Bacterial Count (Streptococcus Mutans) CFU/ml.

**T** =  $T_1$  before application and  $T_2$  after application in the same visit.

**S**= Randomized Controlled Trial, In-Vivo Comparative Study.

Outcome Name	Measuring Unit	Measuring Device
Bacterial count of (Strepto. Mutans)	CFU/ml	Digital Colony Counter, Agar Diffusion test

**Research question:**

Is the application of Nano Silver Fluoride solution after partial caries removal- compared to the Chlorhexidine- will minimize the bacterial count in dentin in permanent class I carious molars?

**I. Materials:**

1. Nano silver fluoride solution (Prepared in Nanotech Co., Egypt) based on silver nanoparticles, chitosan and fluoride. Each tooth will receive two drops of NSF with a micro brush, equivalent to a dose of 10 mg of the solution
2. Chlorhexidine digluconate 2 % solution (Cavity Cleanser, Bisco, USA). Moistens dentin surface after cavity preparation using a micro brush.
3. Rubber dam.
4. Hand spoon excavators.
5. High speed contra angle air-driven hand-piece.
6. Round and round end cylinder carbide and diamond burs.
7. Universal adhesive (Tetric® N-Bond Universal, Ivoclar Vivadent, Schaan, Liechtenstein). The adhesive will be scrubbed into the tooth surface for at least 20 seconds. Followed by dispersing with oil- and moisture-free compressed air until a glossy, immobile film layer results. Light-cure for 10 seconds using a light intensity of  $\geq 500 \text{ mW/cm}^2$ .
8. Bulk-fill resin composite (Tetric® N-Ceram Bulk Fill, Ivoclar Vivadent, Schaan, Liechtenstein) placed in increments of up to 4 mm and cured in 10 seconds ( $\geq 1,000 \text{ mW/cm}^2$ ) or 20 seconds ( $\geq 500 \text{ mW/cm}^2$ ).
9. Medium, fine and extra fine finishing diamond stones and rubber polishing disks.

## **II. Methods:**

## **II.1. Study setting**

This clinical study will be held in the Clinic of Conservative Dentistry Department, Faculty of Dentistry, Cairo University, Egypt. The researcher will bear ultimate responsibility for all activities associated with the conduct of a research project including recruitment of patients, explaining and performing the procedures to them.

## **II.2. Eligibility criteria:**

### **II.2.a. Eligibility Criteria of participants:**

#### **➤ Inclusion Criteria of participants:**

1. 18 – 40 years.
2. Not received antibiotic therapy since 1 month before sampling.
3. Males or Females.
4. Good oral hygiene.
5. Co-operative patients approving the trial.

#### **➤ Exclusion criteria of participants:**

1. Pregnancy.
2. Systemic disease or severe medical complications.
3. Heavy smoking.
4. Xerostomia.
5. Lack of compliance.

### **II.2.b. Eligibility Criteria of teeth:**

➤ **Inclusion Criteria of teeth:**

1. Class I deep caries lesions in permanent molar (reaching  $\geq 1/2$  of the dentin on radiographic examination).
2. Absence of spontaneous pain; negative sensitivity to percussion; and absence of periapical lesions (radiographic examination).

➤ **Exclusion criteria of teeth:**

1. Class II caries lesion.
2. Shallow or enamel caries.
3. Cuspal loss or caries beneath the gingival margin.

**II.3. Variables of the study:**

**Table (1) Variables of study**

Variable	Symbol	Refers to
Intervention	I	Nano silver fluoride solution
	C	Chlorhexidine 2 %
Time of dentin sample collection	T 1	Before the application
	T 2	After the application

**II.4. Trial Description:**

#### **II.4.a Excavation protocol:**

[figure not shown]
The teeth of the patients that meet inclusion criteria will be anesthetized, isolated with a rubber dam. Cavity opened using conventional high-speed rotary instruments. The central cariogenic biomass and the superficial parts of the necrotic dentine will be removed with round burs. Caries lesion will be completely removed in the enamel/dentin junction. The excavation procedure will be terminated as soon as the soft and wet dentine was removed and the remaining tissue was leathery but not hard on exploring. A dentinal sample will then be collected from the base of the cavity using sterile spoon excavator as a baseline for bacteriological assessment. Then, application of either intervention or control agent, another dentinal sample will be collected using a sterile excavator and transferred into sterile tubes and transferred to the laboratory for microbiological analysis.

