#### **II.4.b Assessment of Outcome:**

Samples of carious dentine will be collected with sterile excavator before and after application of intervention/control agent. The dentine samples will be transferred to sterile container containing a 1mL thioglycollate medium used as a carrier, then this sterile container will be kept in an ice box and taken to the microbiology laboratory for processing, within an hour, by another examiner who is blinded to the type of agent applied after partial caries removal. Samples will be vortexed for two minutes, decimally diluted and 0.1 ml will be plated on Mitis Salivarius Bacitracin agar plates, these plates will be incubated anaerobically for 48 hour at 37°C then aerobically for 24 hour at room temperature. The number of colonies will be expressed as colony-forming units (CFU/ml) compared before and after application of the antibacterial agent.

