## II.5. Participant timeline:

All clinical procedures will be carried out at the same visit.

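### The before/after change within an arm cannot separate the agent's effect from the effect of scraping the dentine twice, so it cannot by itself show antibacterial action; the randomized comparison between arms stays valid.

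*Combined protocol and SAP*

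**What the plan says.** **Sampling.** II.4.a describes the baseline sample: "A dentinal sample will then be collected from the base of the cavity using sterile spoon excavator as a baseline for bacteriological assessment". After the agent is applied, "another dentinal sample will be collected using a sterile excavator and transferred into sterile tubes". The text does not say whether T2 comes from the same spot as T1, how deep it goes, or how much is taken. II.5 places everything in one sitting: "All clinical procedures will be carried out at the same visit".

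**Measurement.** II.4.b states: "The dentine samples will be transferred to sterile container containing a 1mL thioglycollate medium used as a carrier". Weighing the sample is not described, and counts are given per ml of suspension rather than per mg of dentine. The same section says the counts will be "compared before and after application of the antibacterial agent".

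**Arms.** PICOTS and Table 1 in II.3 list nano silver fluoride (NSF) and 2% chlorhexidine. There is no inert or untreated arm.

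**Aim and tests.** The Rationale says: "The purpose of this study is to evaluate the antibacterial effect of nano silver fluoride solution on the carious dentin". The Research question also asks about lowering the count in dentine, compared with chlorhexidine. The Trial framework entry reads "Equivalence trial". The null hypothesis, the sample size in II.6 and the tests for numeric data in II.12 (Student's t, Mann-Whitney) all compare the two groups. II.12 names no paired test, and it does not say whether the variable analysed is the T2 count or the change from T1.

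**The concern.** Taking T1 removes some of the tissue that T2 is meant to measure. T2 may then differ from T1 for reasons unrelated to the agent: the first scrape took the more heavily colonised part, the second reached a different depth, or the two scrapes collected different amounts. With no inert arm, nothing in the design measures these effects.

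Two conclusions are at risk. The first is that a fall from T1 to T2 within an arm shows that the agent killed bacteria. The outcome section invites this reading by planning the before/after comparison in a study whose stated purpose is an antibacterial effect. The second is that similar results in the two arms show NSF to work as well as chlorhexidine. Two arms that share a fall due only to sampling would also look alike. The equivalence label makes similarity a result that could be read as success.

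**Working it through.** **1. The plan's own figure.** Inputs from II.6: difference 2.1, SD 2.2 (both × 10³ CFU/mL), power 80%, significance level 5%. II.12 makes tests two-sided.

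n per arm = 2 × (1.960 + 0.842)² × (2.2 / 2.1)² = 2 × 7.85 × 1.098 = 17.2, rounded up to 18.

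This matches the stated 18. The exact t calculation gives 79.5% power at 18 and 87.1% at 22. The step to 22 allows for 1 − 18/22 = 18% losses. A paired calculation with the same two numbers would need only 11 teeth (81.4% power), so the stated size belongs to a comparison between arms.

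**2. Within-arm test when the liquid is inert.** The documents give no sampling-only fall, so g below is an assumption. Also assumed: SD 2.2 at both T1 and T2, T1–T2 correlation ρ from 0 to 0.8, normal data and 18 teeth in the arm.

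- SD of change = 2.2 × √(2(1 − ρ)), which is 3.11, 2.20 and 1.39 for ρ = 0, 0.5 and 0.8.
- Noncentrality = g × √18 / SD of change. For g = 1.0 this is 4.243/3.11 = 1.36, 4.243/2.20 = 1.93 and 4.243/1.39 = 3.05.

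Chance that a two-sided 5% paired t-test is significant, from the noncentral t distribution with 17 degrees of freedom:

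| Sampling-only fall g (× 10³ CFU/mL) | ρ = 0 | ρ = 0.5 | ρ = 0.8 |
|---|---|---|---|
| 0 | 5% | 5% | 5% |
| 0.5 | 10% | 15% | 30% |
| 1.0 | 25% | 44% | 82% |
| 2.1 | 77% | 97% | about 100% |

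With 22 teeth, g = 1.0 gives 30%, 53% and 90%.

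**3. Between-arm test under the same fall.** If both arms fall by g through sampling, the difference in means is (μ₁ − g) − (μ₂ − g) = μ₁ − μ₂, and g cancels. In 40,000 simulated trials with no true difference (18 per arm, ρ = 0.5, g = 0, 1.0 or 2.1), the t-test rejected in 4.9% on change scores and in 5.0% to 5.1% on T2 counts.

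**4. What similar falls can show.** Write the observed falls as g + a in the NSF arm and g + b in the chlorhexidine arm. The between-arm contrast estimates a − b. It is zero when both agents work equally well and also when neither works. Because g is unknown, the size of the falls cannot distinguish the two cases.

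**The case against.** The strongest reply is that the planned inference is between arms. The null hypothesis, the sample size and every named test for numeric data compare NSF with chlorhexidine. II.4.b mentions the before/after comparison but attaches no within-arm test or conclusion to it. A sampling effect common to both arms cancels, as step 3 shows. This stands, and it limits the point to the within-arm change and to claims that either agent is active.

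It can also be said that any active-controlled trial without an inert arm lacks internal proof of activity, however samples are taken. That is true. Here, though, the before/after change is the only internal evidence that might have filled the gap, and the double scrape weakens it.

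A reader might infer three stronger things that the documents do not support.

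- *An inert liquid would necessarily show a fall.* The site and depth of T2 are not stated, no count by depth is given, and samples are not described as weighed, so counts could move either way. A figure in II.4.a was not available to this review and may carry sampling detail. The text supports only that a fall can occur.
- *The NSF-versus-chlorhexidine comparison is biased.* A shared sampling effect does not bias it.
- *Removal of dentine at T1 cuts the trial's power.* If removal scales every count by the same share, mean difference and SD shrink together. The ratio 2.1/2.2 = 0.95 is unchanged, and power at 22 per arm stays at 87%. A loss appears only if the mean is scaled down while the SD is held at 2.2, which the documents give no reason to assume.

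**Conclusion.** The concern holds for the within-arm comparison. The T1-to-T2 change mixes the agent's effect with removal, depth and amount of sample, and the design has nothing to separate them. It cannot by itself support a claim of antibacterial action, and similar falls in both arms would not show that either agent worked.

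The size is conditional. The 25% to 82% at 18 teeth rests on the assumed fall of 1.0 × 10³ CFU/mL, the planning SD of 2.2 × 10³ applied at both times, and correlations of 0 to 0.8. With no sampling-only fall the rate is the nominal 5%. The range shows what could happen and does not estimate what will.

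A between-arm difference, if found, would still be evidence that the two agents affect the counts differently. This is a gap in interpretation and specification that should be closed before analysis. It does not invalidate the trial.

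**What to change.** **Main change, free.** In II.4.b and II.12:

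- make the between-arm comparison of T2 adjusted for T1 the sole inference, by ANCOVA and preferably on log10 CFU/ml, with a rule for zero counts fixed in advance;
- report the T1-to-T2 change within each arm as descriptive only;
- state that no conclusion that either agent lowered the count will be drawn from that change.

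This needs no new data, because T1 is already collected. It also settles which variable II.12 analyses.

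**Optional design change.** In II.4.a, take T1 and T2 from separate parts of the cavity floor, so that T2 does not come from dentine already scraped. Set the T1 site from a random list kept apart from the treatment draw in II.9.b. The operator cannot be blinded once the agent is known, so treatment should still be revealed only after T1 is taken. This adds no samples. The cost is a second short list and some extra noise from variation within a cavity, which makes T1 a somewhat weaker covariate. It has to be decided before sampling starts, because teeth already sampled cannot be corrected.
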